#### **1.3.4. Effects of Inhaled Nitrite and Interaction between Inhaled Nitrite and Background Therapies for PAH**

##### Nitric oxide and nitrite.

NO produced from eNOS is subject to rapid inactivation reactions with hemoglobin that greatly limit its lifetime in blood. Recent studies also indicate that NO formed from eNOS is can be oxidized to nitrite by oxygen or plasma ceruloplasmin. Nitrite transport in blood provides an endocrine form of NO that can be shuttled from the lungs to the periphery, while limiting the exposure of authentic NO to the scavenging red cell environment. Then during the rapid hemoglobin deoxygenation from artery-to-vein, nitrite is reduced back to NO via reactions with hemoglobin, myoglobin, and other heme containing enzymes, such as xanthine oxidoreductase. Once formed, nitrite is a potent vasodilator, potentially regulating basal blood flow and hypoxic vasodilation. Nitrite limits ischemia/reperfusion-induced apoptosis and cytotoxicity in heart, liver and brain. Additionally, nitrite limits hypoxic pulmonary vasodilation in a deoxyhemoglobin- and pH-dependent fashion. Given the central role of NO in vasoregulation, the association of decreased NO bioavailability in PAH and recently emerging signaling actions of nitrite, a strong foundation of knowledge supports that inhaled nitrite can reduce pulmonary pressures in patients with PAH.

**Inhaled nitrite for hypoxia-induced pulmonary hypertension in a new born sheep model.**

[figure not shown]
The above supports that inhaled nitrite could potentially exert the same actions as inhaled NO, by locally generating NO and promoting pulmonary vasodilation. Nitrite therapy has advantages over inhaled NO: ease of administration (intermittent use with a standard nebulizer), better availability, and lower cost. Pre-clinical data from a new-born sheep model of hypoxemia-induced fetal pulmonary hypertension indicate that a single nebulized dose of sodium nitrite produced the same vasodilatory effect as 20 ppm inhaled NO (Figure 1). From this, we hypothesize that (a) low-dose, nebulized nitrite can reduce pulmonary artery pressures and pulmonary vascular resistance in patients with PAH.

**Nitrite reverses experimental mouse hypoxia-induced PAH.**

[figure not shown]
Chronic exposure of mice to hypoxia (10% O2) results in pulmonary vascular remodeling, characterized by increased muscularization, increased right ventricular pressures (RVP) and right ventricular hypertrophy. Treatment with low concentrations of nebulized nitrite (dosing and delivery as described in experimental plan), either once or three times per week, significantly prevented the development of PAH, as defined by all outcome measurements (Figure 2, A-C). Additionally, nitrite treatment 2 weeks into the hypoxic exposure, after the establishment of PAH, halted the progression of PAH and reversed increases in right ventricular pressures. Thus, inhaled nebulized nitrite inhibited both the development of hypoxia-induced PAH and reversed established PAH.

**Nitrite reverses monocrotaline-induced PAH.**

[figure not shown]
To determine whether the effects of nitrite therapy on PAH were specific to chronic hypoxia, we examined an additional model of experimental PAH, sodium monocrotaline (MCT)-induced PAH. Similar to its effects in the hypoxia model of PAH, nitrite reduced monocrotaline-induced PAH (Figure 3 A-D). Nitrite treatment significantly reversed monocrotaline-induced right ventricular hypertrophy and protected against increases in right ventricular pressures.

**Figure 1.** Vasodilatory Effects of Nitrite During Hypoxia-Induced Pulmonary Hypertension

**Fig.2. Nitrite prevents and reverses hypoxia (10% O2) induced pulmonary hypertension.** Nitrite treatments were 1X per week, 3X per week, and when administered after PAH development in week 3 and 4.

**Fig. 3. Nitrite reverses monocrotaline-induced pulmonary hypertension in rats with treatment 3X per week.** A. Reduction in RV mass. B. Reduction in RV mass to body mass. C. Reduction in RV pressure. D. a) control, b) vehicle treated rat with PAH showing hypertrophied right ventricle (RV), c) nitrite treated with normal RV.

### 1.3.5 Rationale for Dose of Nitrite

The low doses of nitrite used in these treatment regimens – less than 45 mg or 13% of the dose used in the emergency treatment of cyanide poisoning – do not produce methemoglobin levels greater than 3% and have not been associated with clinically significant hypotension. Aires Pharmaceuticals, who licensed intellectual property pertaining to inhaled nitrite from the NIH, has completed a Phase 1a single dose escalation study designed to define the maximum tolerated dose of inhaled sodium nitrite delivered to normal volunteers following electronic nebulization. These data, presented in abstract form at the 2009 ATS meetings, show that at the highest dose (176 mg) a significant decrease in systemic blood pressure and increase in heart rate was found. At the maximal tolerated dose (MTD);(125 mg) there was an increase in HR (+24 +/-5 bpm) without significant changes in systolic (-3 +/- 2 mmHg) or diastolic (-3 +/- 2 mmHg) blood pressure. Bioconversion of nitrite was demonstrated by an increase in exhaled NO. Methemoglobin levels increased at the highest doses administered, but remained less than 3.5% in all subjects. Pharmacokinetic modeling demonstrated dose-proportional increases in peak and AUC plasma nitrite.

Note that in 80 volunteers in phase I studies at the NIH methemoglobin levels never rose higher than 3%. If levels of methemoglobin rise above approximately 30% of total hemoglobin, a subject may appear cyanotic and experience dyspnea, due to the reduced oxygen carrying capacity of hemoglobin (methemoglobin cannot bind oxygen). Levels above 50% can cause seizures, hypotension, coma and death.

The effects of the interaction between FDA approved oral therapies for PAH (ETRA and PDE-5i) and inhaled nitrite are unknown. It is possible that the combination of the drugs

could lower systemic blood pressure to potentially clinically significant levels. This is of particular concern for the PD5 inhibitors which will increase the levels of cGMP for any given dose of NO or nitrite. For this reason the doses have been reduced significantly below the MTD of 125 mg and a dose escalation plan will be followed with clear stopping rules. The patient will be carefully monitored with a pulmonary artery catheter during drug administration and intravenous fluids and vasopressors will be immediately available for the treatment of symptomatic hypotension. In addition we propose a dose escalation regimen to ensure careful drug dose titration.

#### **1.4 SIGNIFICANCE**

Inhaled nitric oxide has been demonstrated to improve pulmonary hemodynamics acutely in subjects with pulmonary hypertension. It has been demonstrated to lower pulmonary arterial pressure acutely in preclinical models of pulmonary hypertension, putatively through a mechanism of sustained NO release. Repeat dosing of inhaled sodium nitrite has also been demonstrated to result in sustained improvement in pulmonary hemodynamics and in pulmonary vasculopathy in animal models of pulmonary hypertension.

We hypothesize that inhaled nitrite provides an innovative therapeutic approach for patients with PAH for the following reasons:

- 1) Inhaled nitrite therapy provides a potent, effective treatment that will vasodilate the pulmonary circulation (reduce pulmonary vascular resistance), reduce mean pulmonary artery pressure, and increase cardiac output.
- 2) This study will provide valuable efficacy and safety insights into the interactions between NO and nitrite, both direct NO generators, with or without background PH therapy, particularly PDE5I, on pulmonary hemodynamics and right heart function.
- 3) This study will also provide novel assessments of right ventricular global myocardial function.
- 4) The results obtained from this study will also lay the groundwork for future large-scale clinical trials that are needed to investigate the efficacy of inhaled nitrite and/or its long-term effects on pulmonary hemodynamics in patients with pulmonary hypertension.

## **2. STUDY DESIGN AND METHODS**

### **2.1 CLASSIFICATION AND METHODOLOGICAL DESIGN**

This is a single-center, open label phase II study to evaluate the effect of inhaled nitrite delivered in a dose escalation manner on the change in pulmonary vascular resistance (PVR) in subjects with pulmonary arterial hypertension undergoing right heart catheterization.

### **2.2 STUDY DESIGN AND METHODS**

#### **2.2.1. Study Design**

A total of 50 subjects with a confirmed diagnosis of pulmonary hypertension and meeting all inclusion/exclusion criteria will be enrolled in the study which will entail a single right heart catheterization. The study population consisted of subjects with WHO group I PAH (n=20), WHO group II (n=20) and subjects with WHO group III PH (n=10) will receive the following dose escalation paradigm: Each subject will receive a starting dose of 45 mg inhaled nitrite

(AIR001 Inhalation Solution), with one subsequent planned dose escalation of 90 mg inhaled nitrite, based on pulmonary vascular resistance response and safety and tolerability.

Screening (Day 0):

The potential study subjects are followed on a routine basis in the UPMC Heart and Vascular Institute (HVI), Comprehensive Lung Center (CLC) or an inpatient at UPMC Presbyterian, are well known or referred to the study investigator. Initial screening evaluations including physical examination, medical history, and clinical laboratory assessments will be conducted to determine study eligibilities during a routine clinic visit at the UPMC HVI, CLC or inpatient at UPMC Presbyterian. Subjects who meet the inclusion criteria and none of the exclusion criteria will be entered into the study.

Experimental Procedures (Day 1):

The study visit will occur on the same day subjects are scheduled for their clinically indicated right heart catheterization or who volunteer for a research right heart catheterization for this specific study. Subjects on oral background PAH therapy (ETRA or PDE5I) will be instructed to hold their regimen on the day of the study visit.

Subjects will be evaluated for additional medical history, physical examination, vital signs and pulse oximetry since screening. Laboratory testing will be repeated if baseline laboratory values are clinically significant and warrant repeat testing or inadvertently not collected at the screen visit. An echocardiogram with documentation of TRV for estimation of right ventricular systolic pressure and assessment of LV systolic and diastolic function will be performed pre and post nitrite inhalation.

Right heart catheterization is performed routinely as a clinical standard of care procedure for diagnostic purposes in this disease population. The standard right heart catheterization is performed with a balloon tipped, flow-directed pulmonary artery catheter (Swan-Ganz catheter), inserted through a sheath in the internal jugular vein. As per standard clinical protocol, hemodynamic recordings of right atrial, right ventricular, and pulmonary artery pressures, in addition to cardiac output, are made at baseline, and then repeated following pulmonary vasodilator challenge with inhaled nitric oxide (iNO, which is part of the standard clinical right heart catheterization when assessing pulmonary hypertension). Responses to 40 ppm iNO will be measured before nitrite nebulization to assess vasodilator responsiveness. As a part of this protocol the subjects may undergo an additional hemodynamic measurement using a micromanometer pressure catheter that may be inserted via the Swann-Ganz catheter distal port. Measurements with micromanometer and/or Swann-Ganz catheter will be made with simultaneous flow velocity from transthoracic echocardiographic doppler ultrasound at baseline just prior to nebulized AIR001 administration and at the time of the final hemodynamic assessment (60 minutes after second dose). This portion of the study that involves the micromanometer instrumentation is expected to add an additional 5-10 minutes onto the procedure.

Subjects will receive nebulized AIR001 doses escalated based upon safety and tolerability. The dose of inhaled nitrite will be delivered via electronic nebulizer. During the study right heart/pulmonary artery hemodynamics will be measured as well as noninvasive systemic blood pressure monitoring. Subjects will be tested for the changes in pulmonary vascular resistance (PVR) using standard clinical protocol hemodynamic recordings of right atrial, right ventricular, and pulmonary artery pressures, in addition to cardiac output at time zero, and approximate timelines 15, 30, 45 and 60 minutes after completion of each nebulization dose. For details, see sections 2.10.2 and 2.12 below.

Subjects will be monitored closely for changes in blood pressure during the study. A decrease in systolic blood > 30 mm Hg drop from pre-dose baseline AND symptomatic or requiring fluid replacement or other therapy will lead to a discontinuation of the study treatment, and the next higher dose of inhaled nitrite will not be administered. Subjects will continue to be monitored closely and treated as needed.

Oxygen saturation measured by pulse oximeter and methemoglobin levels monitored by co-oximetry prior to dose administration and through 2 hours post-last dose will be monitored closely. Venous methemoglobin levels may be assessed periodically at investigator discretion. Due to circumstances unknown, co-oximetry may not read MetHgb level, in the event, venous methHgb may be collected at approx. time intervals 30 and 45 minutes for each inhaled dose.

Blood samples may be collected for Cyclic Guanosine Monophosphate (cGMP) concentration determination, pharmacokinetics (PK) and platelet mitochondrial analysis at pre dose and the end of the peak dose of nitrite may be collected. PK and cGMP measurements will be made on mixed venous blood using PCW pullback samples and venous blood will be collected for platelet mitochondrial analysis

Subjects will be monitored carefully for adverse events, laboratory test abnormalities, and changes in vital signs. Adverse experiences will be evaluated according to criteria outlined in the NCI Common Terminology Criteria for Adverse Events (CTCAE), version 4.0.

Following the study treatment, subjects will be followed as an outpatient on Day 30 (+/- 5 day window). An additional follow-up assessment by telephone will occur on Day 3.

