	
This is a single-center, open label phase II study to evaluate the effect of inhaled nitrite delivered in a dose escalation manner on the change in pulmonary vascular resistance (PVR) in subjects with pulmonary arterial hypertension undergoing right heart catheterization.
 
A total of 50 subjects with a confirmed diagnosis of pulmonary hypertension and meeting all inclusion/exclusion criteria will be enrolled in the study which will entail a single right heart catheterization. The study population consisted of subjects with WHO group I PAH (n=20), WHO group II PH (n=20) and subjects with WHO group III PH (n=10) will receive the dose escalation paradigm:
 
 
• Each subject will receive a starting dose of 45 mg inhaled nitrite (AIR001 Inhalation Solution), followed by a second dose of 90 mg inhaled nitrite, based on safety and tolerability.
 

The study visit will occur on the same day subjects are scheduled for their clinically indicated right heart catheterization or who volunteer for a research right heart catheterization for this specific study. Subjects on oral background PAH therapy (ETRA or PDE-5I) will be instructed to hold their regular PAH regimen on the day of the study visit.

Baseline pulmonary artery hemodynamic assessment, echocardiogram, micromanometry measured simultaneous pressure and flow velocity signals will be performed prior to inhaled nitrite treatment. Responses to 40 ppm inhaled NO will be measured before nitrite nebulization via a non-rebreather face mask to assess baseline, pre-AIR001 vasodilator responsiveness.

Subjects will receive a starting dose of 45 mg (placed in the nebulizer cup) of inhaled nitrite (AIR001), with one subsequent planned dose of 90 mg of inhaled nitrite, based on safety and tolerability, approximately 60 minutes after the first dose. During the study, right heart/pulmonary artery hemodynamics will be measured continuously, and cardiac output measured at 15 minute intervals, as well as noninvasive systemic blood pressure monitoring. Subjects will be tested for the changes in hemodynamics and calculated pulmonary vascular resistance (PVR) with inhaled nitrite.

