## **2.2 STUDY TREATMENT**

Following initial standard clinical measurements for right heart catheterization, 40 ppm inhaled NO gas will be administered for approximately 5-15 minutes through a facemask, continuously monitoring subject vasoreactivity. This is considered part of the clinical right heart catheterization procedure for pulmonary hypertension. Repeat hemodynamic measurements will be performed upon completion of inhaled NO. Pre-dose baseline PK and methemoglobin levels may be collected. The inhaled nitrite will be delivered per protocol below.

Following completion of all baseline assessments, each subject will receive a starting dose of inhaled nitrite, with one subsequent planned dose escalation of inhaled nitrite, based on safety and tolerability. Subjects will be monitored carefully during and after the study treatment.

The study will be conducted at UPMC Presbyterian Hospital, 3rd FL Catheterization Laboratory. Baseline vasoreactivity will be recorded after Inhaled NO at 40 ppm for approximately 5-15 minutes. Subjects will receive a starting dose of AIR001 (45 mg), with one subsequent planned dose escalation to 90 mg based upon safety and tolerability. The dose of AIR001 will be delivered by an electronic nebulizer system that is portable, highly efficient utilizing continuously vibrating mesh aerosol generation technology that allows a high percentage respirable dose delivery, minimal loss of drug to the environment between inhalations, and a reproducible droplet size distribution for optimal delivery of drugs to the distal pulmonary tree.

During, and at approximate timelines of 15, 30, 45 and 60 minutes post-inhalation for each dose, right heart/pulmonary artery hemodynamics will be measured as well as noninvasive systemic

blood pressure monitoring. Subjects will be monitored closely during the study. Dose limiting toxicity (DLT) is defined in Table 1.

A dose level will also be considered intolerable if, in the judgment of the Investigator, the type, frequency, or severity of AEs becomes unacceptable. If an intolerable dose is identified, no further doses at that or higher doses will be administered.

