## **2.6. STOPPING RULES**

In addition to the dose limiting toxicity as outlined in Table 1 above, study treatment will be discontinued if any of the following occurs:

- A decrease in systolic BP > 40 mm Hg drop from pre-dose baseline;
- Desaturation > 10% from baseline;
- A single occurrence of venous methemoglobin level >5%;
- Severe DLT criteria met and symptomatic or requiring fluids or treatment;
- Any serious adverse event thought to be possibly related to the study treatment.

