## **2.13. ENDPOINTS**

### **2.13.1. Primary Endpoints**

The primary outcome measures for this study is change in pulmonary vascular resistance (PVR) measured by right heart catheterization from time zero compared with peak effect within 60 minutes post completion of nebulized dose of nitrite.

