### 2.15.2 Statistical Analysis

#### General Approach

The primary efficacy outcome variable is pulmonary vascular resistance (PVR), measured by right heart catheterization. T-test will be performed to determine difference of mean values for outcome variables at baseline and highest tolerated nitrite. The secondary endpoints will be analyzed with repeated measures ANOVA (RM-ANOVA) to compare the overall cardiopulmonary hemodynamic effects and the PK endpoints (eg: AUC) for all doses of nitrite.

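### Section 2.2.1 makes the second dose depend partly on PVR response, other passages on safety and tolerability alone; if the PVR clause is applied, the primary outcome helps decide which dose is analysed

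*Combined protocol and SAP*

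**What the plan says.** Four places state the condition for the second dose.

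- Section 2.2.1, opening paragraph: "based on pulmonary vascular resistance response and safety and tolerability".
- Section 2.2.1, Day 1 text: "Subjects will receive nebulized AIR001 doses escalated based upon safety and tolerability".
- Protocol Synopsis, design description: "followed by a second dose of 90 mg inhaled nitrite, based on safety and tolerability".
- Section 2.2 Study Treatment: "with one subsequent planned dose escalation to 90 mg based upon safety and tolerability".

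The operating criteria are in Table 1 (dose-limiting toxicity) and its footnotes, and in the stopping rules of Section 2.6 ("study treatment will be discontinued if any of the following occurs"), repeated in Section 5.5.2. They cover blood pressure, saturation, methemoglobin, symptoms and adverse events. None mentions PVR.

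The primary endpoint in Section 2.13.1 is the change in PVR "from time zero compared with peak effect within 60 minutes post completion of nebulized dose of nitrite", with no dose named. Section 2.15.2 supplies the dose: "T-test will be performed to determine difference of mean values for outcome variables at baseline and highest tolerated nitrite". Secondary endpoints are compared across all doses by repeated measures ANOVA. PVR components are read at about 15, 30, 45 and 60 minutes after each dose.

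**The concern.** Section 2.2.1 contradicts itself as well as the synopsis and Section 2.2 Study Treatment. Because the PVR clause has no threshold, direction or decision time, two operators could follow it faithfully and escalate opposite patients: one those who responded to 45 mg, the other those who did not.

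The extra criterion is also the primary outcome. Under the clause, a patient may stay at 45 mg because of a PVR reading rather than intolerance, yet still be analysed as if 45 mg were the highest tolerated dose. Patients who go on to 90 mg have been selected on a noisy first-dose reading, and their next reading moves back toward their own mean whether or not the dose matters. That shifts the PVR change at the last dose given and produces an apparent difference between doses.

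**Working it through.** **The plan's own figure.** The plan has none on escalation. Its nearest is the sample size in Section 2.15.1: 14 participants, 80% power, a 10% fall from 911 (91.1 units), paired t-test. With 102 as the SD of the change, a two-sided 5% test needs 12. Exactly 14 results for an SD of change of 108 to 112, for example 102 × √(2 × (1 − 0.4)) = 111.7. The sample size has no bearing on this point.

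**Assumptions, none given in the documents.** True change −10% at both doses (no dose effect); between-patient SD 10 points; reading noise SD 8 or 5 points; independent errors; no noise in the baseline; escalation cut-off at −10% or −20%. Two opposite rules are tried, for illustration only: escalate patients whose fall is smaller than the cut-off, or only patients whose fall reaches it.

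**One reading per dose (closed form).** Let T = √(10² + s²), z = (c + 10)/T and k = s²/T, where s is the noise SD and c the cut-off.

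- Shift in the mean at the last dose given: k × φ(z) in size.
- Apparent second-minus-first difference in escalated patients: −kφ(z)/(1 − Φ(z)) if smaller falls escalate, +kφ(z)/Φ(z) if larger falls escalate.

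For s = 8 and c = −10: T = 12.81, z = 0, k = 64/12.81 = 5.00. The shift is 5.00 × 0.399 = 2.0 points and the difference 2.0/0.5 = 4.0 points.

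**Peak of four readings per dose (the planned endpoint).** The same model, with the lowest of four readings at each dose and the cut-off applied to that peak; simulated with one million patients per setting.

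| Noise SD | Cut-off | Single: shift | Single: difference (smaller / larger falls escalate) | Peak: shift | Peak: difference (smaller / larger falls escalate) |
|---|---|---|---|---|---|
| 8 | −10% | 2.0 | −4.0 / +4.0 | 0.8 | −3.4 / +1.1 |
| 8 | −20% | 1.5 | −1.9 / +6.8 | 1.1 | −1.9 / +2.5 |
| 5 | −10% | 0.9 | −1.8 / +1.8 | 0.4 | −1.3 / +0.6 |
| 5 | −20% | 0.6 | −0.7 / +3.2 | 0.4 | −0.6 / +1.3 |

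The shift is toward a larger apparent fall if smaller falls escalate, and toward a smaller one if larger falls escalate. If everyone escalates, or escalation is unrelated to PVR, both columns are zero.

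**Second model.** Here the drug has no effect, the baseline is one noisy reading, there are four readings per dose and 20 patients, and the cut-off is −10%. With reading SD 5 to 15% of baseline, the peak endpoint shifts by about 0.6 to 2.3 points, again in either direction.

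These shifts are additional to the separate effect of comparing a peak with a single baseline, which is present even when everyone escalates.

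**The case against.** The strongest reply is that the PVR clause is leftover wording. Three of the four statements omit it, no operating criterion uses PVR, Section 1.3.5 ties escalation to hypotension risk, and the PDE-5 inhibitor text in Section 5.1 withholds the next dose for a blood pressure drop. Nor do the documents say that PVR is calculated before the second dose is decided, although the readings would allow it. This stands as far as it goes: a reader might infer a response-driven design, and the documents do not establish one. They do not exclude it either, since the clause sits in the main design paragraph.

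A reader might also infer a large false-positive risk. With one reading per dose, 50 patients, noise SD 8 and a −10% cut-off, a paired t-test of second against first dose rejects about 44% of the time when there is no dose effect. The plan contains no such test. Its t-test is baseline against highest tolerated dose, its endpoint is a peak, and its power statement concerns about 20 Group I patients. With peak of four, the rejection rate of that unplanned test is about 11 to 31% at 50 patients and 6 to 13% at 20. None of these is the error rate of a planned analysis.

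Finally, none of the six specific aims compares 45 mg with 90 mg. The dose comparison enters only through the secondary repeated measures ANOVA, which limits what is at stake there.

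**Conclusion.** The contradiction is certain and can be read directly from the text. The bias is conditional: it arises only if the PVR clause is applied. In that case the analysis at the highest tolerated dose becomes an analysis at a dose chosen partly by the outcome.

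On the stated assumptions, the planned peak endpoint shifts by about 0.4 to 1.1 points and the apparent dose difference by about 0.6 to 3.4 points. A single reading per dose gives about 0.6 to 2.0 and 0.7 to 6.8 points. Against the planned 10% effect, the peak shift is about 4 to 11% of the target (0.4/10 to 1.1/10). Confidence in these sizes is limited, because noise, between-patient spread and cut-off are all assumed.

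It would go too far to say that the primary result will be biased, or that any bias favours the drug. The documents show neither that the clause is used nor which patients it would escalate.

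**What to change.** 1. Reconcile the synopsis, both statements in Section 2.2.1 and Section 2.2 Study Treatment so that one escalation rule applies throughout. The choice of rule is the sponsor's.
2. For each patient not escalated, record whether the reason was dose-limiting toxicity, other tolerability or PVR response.
3. If PVR response stays a criterion:
   - State its threshold, direction and decision time.
   - Do not read the t-test at the last dose given as an effect at the highest tolerated dose.
   - Analyse all first- and second-dose PVR readings in a likelihood-based mixed model, rather than comparing escalated patients only. Selection on recorded first-dose readings can then be ignored, provided those readings are all in the model and the model is adequate.
   - Report the first-dose change in all patients alongside, as a sensitivity analysis. Making it the primary contrast would change the quantity being estimated and is not needed.

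Items 1 and 2 cost about one sentence and one worksheet field. Item 3 needs a revised analysis section, and only if the criterion is kept.
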